## 1.0 TRIAL SUMMARY

Abbreviated Title	PembroX
Trial Phase	II
Clinical Indication	Non-small cell lung cancer, resectable
Trial Type	Randomized phase II
Type of control	Control arm of randomized schema
Route of administration	Intravenous
Trial Blinding	No
Treatment Groups	(1) Pembrolizumab followed by surgery (2) Stereotactic radiation therapy and pembrolizumab followed by surgery
Number of trial subjects	40
Estimated enrollment period	9 months: 4 patients per month
Estimated duration of trial	25 months
Duration of Participation	15 months
Estimated average length of treatment per patient	3 months, 12 months follow-up

## 2.0 TRIAL DESIGN

### 2.1 Trial Design

This is a randomized single-institution, phase II, open-label clinical trial of neoadjuvant pembrolizumab with or without low-dose stereotactic radiation therapy (SRT) in stage I- IIIA non-small lung cancer (NSCLC) patients who are planned to undergo surgical resection of their lung cancer.

Two consecutive run-in cohorts will administer pembrolizumab or pembrolizumab with SRT of 12 Gy to the lateral aspect of the primary tumor. Patients will receive pembrolizumab for 2 cycles prior to surgery or SRT and surgery. Surgical resection of all involved areas of tumor will occur within 6 weeks of the last administration of pembrolizumab. It should be noted that in almost all cases, surgery is expected to occur very expeditiously, within a much shorter window and 6 weeks would represent only the greatest allowable amount of delay.

If during the run-in, only the pembrolizumab-alone cohort meets pre-specified safety parameters, subsequently enrolled patients will enter a larger expansion cohort, with treatment given according to that cohort only. If during the run-in both cohorts meet pre-specified safety parameters, subsequently enrolled patients will enter the expansion cohort and be randomized between preoperative pembrolizumab versus pembrolizumab with SRT of 12 Gy.

Patients will be followed every 12 weeks for 1 year for disease status and survival.

### 2.2 Trial Diagram

Two consecutive run-in cohorts will be treated establishing the safety of neoadjuvant pembrolizumab and pembrolizumab-SRT delivered in the preoperative window. An expansion cohort will include a larger number of patients who will be treated with pembrolizumab alone or be randomized between the two arms.

**Cohort 1:** 6 patients. The patients will undergo 2 cycles of pembrolizumab prior to surgery. Surgery will occur no later than 6 weeks following the last dose of pembrolizumab.

If  $\leq 33\%$  of patients experience grade 3 immune-related toxicity attributable to study interventions (as determined within 30 days of date of surgery), or  $\leq 1$  patient progresses to unresectability over the course of study treatment, proceed to Cohort 2.

If  $>33\%$  of patients experience grade 3 immune-related toxicity attributable to study interventions (as determined within 30 days of date of surgery), or  $> 1$  patient progresses to unresectability over the course of study treatment, the study will terminate.

**Cohort 2:** 6 patients. The patients will undergo 2 cycles of pembrolizumab then within the week (7 days  $\pm$  3 days) following administration of the second cycle, a single fraction of SRT (12 Gy) will be delivered to 50% of the primary tumor only. Definitive surgical resection will occur

[figure not shown]
no later than 6 weeks following the last dose of pembrolizumab.

If  $\leq 33\%$  of patients experience grade 3 immune-related toxicity attributable to study interventions (as determined within 30 days of date of surgery), or  $\leq 1$  patient progresses to unresectability over the course of study treatment, proceed to Expansion Cohort (randomization between parameters of Cohort 1 and Cohort 2, e.g. randomization between preoperative pembrolizumab versus pembrolizumab and SRT).

If >33% of patients in Cohort 2 experience grade 3 immune-related toxicity attributable to study interventions (as determined within 30 days of date of surgery), or > 1 patient progresses to unresectability over the course of study treatment, then proceed to Expansion Cohort (parameters only of Cohort 1, e.g. preoperative pembrolizumab alone).

**Expansion Cohort:** 28 patients. The patients will be treated according to Cohort 1 if Cohort 2 failed to meet the specified safety milestones. If both cohorts met the safety milestones, then patients in this cohort will be randomized to parameters of either Cohort 1 or Cohort 2. Surgery will occur no later than 6 weeks following the last dose of pembrolizumab.

**Stopping Rule:** If at any point during the study, >15% of patients progress to unresectability over the course of the study treatment, then the study will terminate. This stopping rule will be cumulatively evaluated at all timepoints during the protocol, for all patients enrolled in any phase of the protocol. Each case of study-induced medical unfitness, tumor progression, or any other cause resulting in unresectability will trigger a re-evaluation of the 15% stopping rule.

\* Cycle 2 of pembrolizumab should be given except as recommended per protocol, section 5.2.1.2

\*\* SRT is delivered within 7 days +/- 3 days of second pembrolizumab cycle. If second cycle is not given due to discontinuation, SRT should not be given (patient should continue to surgery)

when deemed safe by treating surgeon).

^ Surgery will take place no later than 6 weeks following last dose of pembrolizumab, e.g. no later than week 7 if only one cycle of pembrolizumab was tolerated, or if two cycles of pembrolizumab were given, week 10.

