#### 3.2 Secondary Objectives & Hypotheses

(1) **Objective:** To assess the safety of preoperative pembrolizumab +/- SRT when combined with surgery;

**Hypothesis:** In patients scheduled for NSCLC resection, pembrolizumab, or pembrolizumab + SRT, given in the preoperative window, will meet safety criteria described by the protocol;

(2) **Objective:** To record the toxicity of preoperative pembrolizumab +/- SRT when combined with surgery, according to CTCAE v. 4, including immune-related adverse events (AEs);

**Hypothesis:** In patients scheduled for NSCLC resection, pembrolizumab, or pembrolizumab + SRT, given in the preoperative window, will result in acceptable short-term and perioperative toxicity;

(3) **Objective:** To determine the 1-year overall survival rate resulting from preoperative pembrolizumab +/- SRT when combined with surgery;

**Hypothesis:** In patients scheduled for NSCLC resection, pembrolizumab + SRT given in the preoperative window will result in a higher 1-year survival rate than pembrolizumab alone;

(4) **Objective:** To determine the 1-year relapse free survival rate resulting from preoperative pembrolizumab +/- SRT when combined with surgery;

**Hypothesis:** In patients scheduled for NSCLC resection, pembrolizumab + SRT given in the preoperative window will result in a higher 1-year relapse free survival rate than pembrolizumab alone;

(5) **Objective:** To determine the 1-year rate of distant metastases resulting from preoperative pembrolizumab +/- SRT when combined with surgery;

**Hypothesis:** In patients scheduled for NSCLC resection, pembrolizumab + SRT given in the preoperative window will result in a lower 1-year distant metastasis rate than pembrolizumab alone;

(6) **Objective:** To assess quality of life associated with preoperative pembrolizumab +/- SRT when combined with surgery;

**Hypothesis:** In patients scheduled for NSCLC resection, pembrolizumab, or pembrolizumab + SRT, given in the preoperative window, will result in acceptable short-term and perioperative quality of life;

(7) **Objective:** To determine the rate of unresectability that results from a program of preoperative pembrolizumab +/- SRT to be followed by a planned surgery;

**Hypothesis:** In patients scheduled for NSCLC resection, either pembrolizumab or pembrolizumab + SRT given in the preoperative window will both result in <15% overall rate of unresectability following the preoperative program;

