#### **4.4 Secondary Objectives & Hypotheses**

Secondary objectives include safety according to criteria described by the protocol ( $\leq 33\%$  grade 3 immune-related toxicity); toxicity according to CTCAE v. 4, including immune-related adverse events (AEs); and quality of life.

Other secondary objectives include the 1-year overall survival rate, 1-year relapse free survival, 1 year rate of distant metastases, and rate of progression to unresectability following the preoperative program. These exploratory data will provide an initial basis for investigating which of these two programs might provide the best overall clinical benefits and merit further study.

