### **5.9 Subject Replacement Strategy**

Patients who drop out before starting pembrolizumab will be replaced. In addition, patients who come off study before completing surgery without grade  $\geq 3$  toxicity will be replaced. The frequency of each of these events will be reported and reasons for replacement reviewed.

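### The toxicity limb of both run-in gates, and the matching safety criterion, name grade 3 immune-related events without saying whether grade 4 and 5 events count

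*Combined protocol and SAP*

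**What the plan says.** Section 2.2 sets two consecutive run-in cohorts of six: Cohort 1 ("6 patients. The patients will undergo 2 cycles of pembrolizumab prior to surgery") and Cohort 2 ("6 patients. The patients will undergo 2 cycles of pembrolizumab then within the week", after which SRT is given). Each has a proceed sentence and a fail sentence, and all four define the toxicity event alike. The limit is 33% "of patients experience grade 3 immune-related toxicity attributable to study interventions (as determined within 30 days of date of surgery"). The Cohort 2 fail sentence reads "If >33% of patients in Cohort 2 experience grade 3 immune-related toxicity attributable to study interventions" and goes on to the same window. Failure in Cohort 1 ends the study. Failure in Cohort 2 sends the 28 expansion patients to pembrolizumab alone instead of randomisation.

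Section 4.4 carries the criterion into the secondary objectives as at most 33% "grade 3 immune-related toxicity".

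The grade is worded differently elsewhere:
- Section 5.9, on replacement, says "In addition, patients who come off study before completing surgery without grade" and continues with 3 or above.
- Section 6.3.2 has every event of grade 3 and higher entered in the database with an attribution.
- Appendix 5, item 3.1, covers grades 3 to 5.
- Table 3 on dose modification treats grade 3 and grade 4 in separate rows for some events.

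On purpose, Section 2.2 says "Two consecutive run-in cohorts will be treated establishing the safety of neoadjuvant pembrolizumab and pembrolizumab-SRT delivered in the preoperative window", and the first secondary objective in Section 3.2 is "To assess the safety of preoperative pembrolizumab +/- SRT when combined with surgery".

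**The concern.** A toxicity gate is normally cumulative in severity: an event worse than the one that counts must also count. Here the words do not say so, and other sections of the same protocol show that its authors write the inclusive form when they want it. Someone applying the gate as written would score a grade 3 colitis and not score a colitis first recorded at grade 4.

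The replacement rule makes the mismatch sharper. A patient who leaves before surgery with a grade 4 immune event is not replaced under the toxicity clause of Section 5.9. That patient therefore stays among the six in the denominator but, read literally, is not in the numerator.

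The gates decide whether the study continues after Cohort 1 and whether SRT is randomised among the 28 expansion patients. Section 4.4 applies the same words to the reported safety objective, so the ambiguity outlasts the run-in.

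**Working it through.** The plan gives no operating characteristics for the gates, so there is no figure of its own to reproduce.

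**1. How one event changes the decision.** The limit is 33% of 6. Two of 6 is 33.3%, which passes if 33% means one third and fails if it is taken strictly. That is a separate ambiguity, so both readings are shown.
- One-third reading: two patients with grade 3 and one with an event recorded only at grade 4 score 2/6 = 33.3% literally (pass), and 3/6 = 50% if all count (fail).
- Strict reading: one patient with grade 3 and one with grade 4 score 1/6 = 16.7% literally (pass), and 2/6 = 33.3% if both count (fail).

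**2. What the other numerical rules catch.** A gate also fails if more than 1 of 6 patients progresses to unresectability. The stopping rule in Section 2.2 ends the study above 15% cumulative unresectability from any cause, including unfitness caused by the study.
- 1/6 = 16.7% exceeds 15%, so one such case among the first six patients meets the stopping rule.
- 1/7 = 14.3% and 1/12 = 8.3% do not; 2/12 = 16.7% and 2/13 = 15.4% do. From the 7th to the 13th patient, two cumulative cases are needed.
- If Cohort 1 had none, a single Cohort 2 patient made unfit for resection by a grade 4 event triggers neither rule.
- Severe events that resolve before surgery, or that occur after resection within the gate's 30 days, are outside both rules.

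**3. Illustration of size.** Let p be the true proportion of patients with an immune-related event of grade 3 or higher, and f the share of those patients who have a grade 3 record that the gate counts. Both are assumed. The counted rate is p × f, and with X ~ Binomial(6, p × f):

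P(X ≥ 3) = 1 − [(1−q)^6 + 6q(1−q)^5 + 15q²(1−q)^4], where q = p × f.

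- p = 0.40, f = 1: 1 − (0.0467 + 0.1866 + 0.3110) = 0.456.
- p = 0.40, f = 0.75, q = 0.30: 1 − (0.1176 + 0.3025 + 0.3241) = 0.256.
- Strict reading, P(X ≥ 2): 1 − (0.0467 + 0.1866) = 0.767 against 1 − (0.1176 + 0.3025) = 0.580.

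Chance that the toxicity limb fails the cohort (3 or more of 6):

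| True rate p | all count (f = 1) | f = 0.75 | f = 0.5 |
|---|---|---|---|
| 30% | 25.6% | 13.2% | 4.7% |
| 40% | 45.6% | 25.6% | 9.9% |
| 50% | 65.6% | 40.4% | 16.9% |
| 60% | 82.1% | 55.8% | 25.6% |

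**4. Low end.** The nearest figure in the documents is KEYNOTE-001 in Section 4.1.2: 47 of 495 patients (9.5%) with adverse events of grade 3 or higher. That was advanced disease, without this regimen, and not only immune events. At p = 0.095 and f = 0.75, q = 0.071, and P(X ≥ 3) goes from 1.4% to 0.6%.

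**The case against.** Grade 3 may be loose shorthand for grade 3 or higher. Section 5.9 keeps patients with grade 3 or higher toxicity in the cohort, which fits a gate meant to count them. Section 6.4.8.4 records each change of grade within an episode, so a grade 4 event that passed through grade 3 may also have a grade 3 record. This narrows the literal gap to events with no grade 3 record, and it makes an inclusive intent plausible. It does not settle the matter, because neither Section 2.2 nor Section 4.4 says so or refers to those records.

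The protocol also has other oversight. Section 5.10 allows termination for the incidence or severity of adverse reactions, Section 6.3.4 provides committee review, and Appendix 5 (Review of Adverse Event Rates) requires a report if grade 3 or 4 rates exceed the brochure or label. A fatal event would hardly go unnoticed. These provisions stand as safeguards, but they set no toxicity threshold and do not alter the gate's result.

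A reader might infer that six of six patients with grade 4-5 immune events would simply pass, or that the gate is the trial's only numerical safety rule. The documents do not support either in that form. The six-of-six case meets the toxicity limit only if the events have no grade 3 record. It avoids the unresectability rules only if the patients are still resected or the events come after surgery. The 15% rule is numerical, continuous and expressly includes treatment-caused unfitness.

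A reader might also call the restriction to immune-related events an error. It is largely a design choice. Objective 2 in Section 3.2 covers overall and perioperative toxicity separately, and an SRT-attributed event does count if it is grade 3 and judged immune-related. What remains is narrow: non-immune SRT injury that does not prevent resection.

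**Conclusion.** The point stands as a defect of wording in a go/no-go rule. As written, the toxicity limb of both gates and the criterion in Section 4.4 leave out grade 4 and 5 immune-related events with no grade 3 record, while less severe events count. One such event is enough to reverse a cohort's result on either reading of 33%.

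The average effect depends on rates that the documents do not give. It is a drop from 45.6% to 25.6% in the chance of exceeding 2 of 6 under the assumed 40% rate with a quarter of affected patients uncounted, and under one percentage point if severe events are as rare as in KEYNOTE-001. The calculation assumes independent patients and that the uncounted patients have no grade 3 record at all. The cohort size is a limit of its own: with every event counted, a true rate of 40% still passes 54.4% of the time.

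The documents do not show that the gates would in practice pass an unsafe regimen unnoticed, and this point does not claim it.

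**What to change.** Reconcile the grade wording at five places (the four gate sentences in Section 2.2 and the criterion in Section 4.4) with Sections 5.9 and 6.3.2 and Appendix 5, item 3.1. The gate should state which grades count and should not leave out events more severe than those it counts. It should also say how a patient retained under Section 5.9 because of toxicity enters the numerator.

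As a secondary point, state whether non-immune events attributed to SRT count toward the limit, since Section 2.2 says that the run-in establishes the safety of pembrolizumab with SRT. Either answer can be defended if it is written down; the choice is the sponsor's.

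The cost is a short amendment. No new data are needed, because events of grade 3 and higher are already recorded with attribution. The downside is that a cohort may be somewhat more likely to fail. For example, at an assumed true rate of 20% with a quarter of affected patients uncounted (0.20 × 0.75 = 0.15), counting all of them raises the chance of 3 or more of 6 from 4.7% to 9.9%.

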patients, and 23.3 months (range, 1.0–23.3) in treatment-naïve patients. At the data collection cutoff (August 2014), the median duration of PFS was 3.7 months [95% CI, 2.9–4.1] in all patients (3.0 months [95% CI, 2.2–4.0] in previously treated patients, and 6.0 months [95% CI, 4.1–8.6] in treatment-naïve patients), and the median duration of OS was 12.0 months [95% CI, 9.3–14.7] in all patients (9.3 months [95% CI, 8.4–12.4] for previously treated patients and 16.2 months [95% CI, 16.2—not reached] for previously untreated patients) (Garon 2015). For adverse events (AEs) considered to be treatment related, fatigue, pruritus, and decreased appetite were the most common AEs and occurred in 10–20% of all patients. There was no clear difference between the incidence of AEs and the dose/schedule of pembrolizumab. AEs of grade 3 or higher were reported in 47 of 495 patients (9.5%). Immune-related AEs occurred in ≥2% of patients including hypothyroidism ( $n = 34$ , 6.9%), hyperthyroidism ( $n = 9$ , 1.8%), infusion-related reaction ( $n = 10$ , 2%), and pneumonitis ( $n = 18$ , 3.6%). There was a single case of grade 5 interstitial lung disease that resulted in death (Garon 2015).

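### Both run-in safety gates join their limits with *or* in the proceed and the stop sentence, so a toxicity-only breach triggers opposite actions

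*Combined protocol and SAP*

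**What the plan says.** Section 2.2 (Trial Diagram) sets a gate after each run-in cohort of 6 patients. Each gate has two limits: the share of patients with attributable grade 3 immune-related toxicity (33%), and the number who become unresectable (one).

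- **Cohort 1, proceed:** toxicity at most 33%, *or* at most one "patient progresses to unresectability over the course of study treatment, proceed to Cohort 2".
- **Cohort 1, stop:** toxicity above 33%, *or* more than one "patient progresses to unresectability over the course of study treatment, the study will terminate".
- **Cohort 2, proceed:** the same two limits, again joined by *or*, lead to "proceed to Expansion Cohort (randomization between parameters of Cohort 1 and Cohort 2".
- **Cohort 2, fail:** the sentence opens "If >33% of patients in Cohort 2 experience grade 3 immune-related toxicity attributable to study interventions", adds *or* more than one unresectable patient, and ends "then proceed to Expansion Cohort (parameters only of Cohort 1, e.g. preoperative pembrolizumab alone".

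The same section has a study-wide stopping rule: if at any point ">15% of patients progress to unresectability over the course of the study treatment, then the study will terminate". On its scope it adds: "This stopping rule will be cumulatively evaluated at all timepoints during the protocol, for all patients enrolled in any phase of the protocol".

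Three other places bear on intent. Section 2.1 and the Expansion Cohort paragraph of 2.2 refer to cohorts meeting, or failing to meet, safety parameters or milestones. Section 4.4 cites the 33% grade 3 limit as the protocol's safety criterion. None says whether both limits must hold. Section 7, the statistical analysis plan, does not restate the gates.

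**The concern.** The opposite of *A or B* is *not A and not B*. If the stop sentence is *toxicity breached or unresectability breached*, the proceed sentence has to be *toxicity met and unresectability met*. With *or* in both, every cohort that breaches exactly one limit satisfies both sentences.

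The Cohort 1 gate decides whether the study ends. The Cohort 2 gate decides whether the 28 expansion patients may be randomised to SRT. The trial is open label (Section 5.2.3), so where the text supports both actions, the reading would be chosen with the toxicity counts in view. A gate meant to fix the decision in advance would not do so in the case it exists for, which is excess toxicity.

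**Working it through.** The documents give no operating characteristics for the gates, so there is no stated figure to reproduce.

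**1. Logic, gate text alone.** Let t be the number of 6 with grade 3 immune-related toxicity and u the number of 6 unresectable. Each runs from 0 to 6, giving 7 × 7 = 49 outcomes. The 33% limit can be read in two ways, because 2/6 = 33.3% is literally above 33% but equals one third.

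| Reading of 33% | Proceed only | Stop only | Both | Neither |
|---|---|---|---|---|
| 2/6 is a breach | 4 | 25 | 20 | 0 |
| 2/6 is allowed | 6 | 20 | 23 | 0 |

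The 20 conflicts are 5 × 2 = 10 toxicity-only breaches and 2 × 5 = 10 unresectability-only breaches. The 23 are 4 × 2 = 8 and 3 × 5 = 15. With *and* in the proceed sentence, no outcome meets both.

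**2. What the 15% rule settles.**

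- Two unresectable patients in Cohort 1: 2/6 = 33.3%, so the study terminates.
- Two in Cohort 2 after none in Cohort 1: 2/12 = 16.7%, so the study terminates.
- One in Cohort 1: 1/6 = 16.7%, so the study terminates.
- One in Cohort 2 after none in Cohort 1: at most 1/7 = 14.3%, falling to 1/12 = 8.3%, so the study continues.

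Unresectability-only conflicts are therefore resolved. What remains is a toxicity breach with u = 0 in Cohort 1, or with at most 1 of the 12 run-in patients unresectable by the end of Cohort 2.

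The same arithmetic shows the gates disagreeing with the 15% rule. The Cohort 1 gate tolerates one unresectable patient, yet 1/6 terminates. The Cohort 2 gate sends two unresectable patients to a pembrolizumab-alone expansion, yet 2/12 terminates.

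**3. How often the conflict would arise.** Assumptions: toxicity and unresectability are independent; unresectability is 5%; true toxicity is 9.5%, 20% or 30%. The 9.5% is the grade 3 or higher rate of 47/495 in Section 4.1.2 (KEYNOTE-001). It covers advanced disease without SRT or surgery and is not limited to immune-related events, so it is a reference point only. The other rates are assumed.

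Binomial, n = 6:

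- P(t ≥ 2) = 0.1046 / 0.3446 / 0.5798
- P(t ≥ 3) = 0.0138 / 0.0989 / 0.2557
- P(u = 0) = 0.95^6 = 0.7351
- P(u = 1) = 6 × 0.05 × 0.95^5 = 0.2321
- P(u ≤ 1) = 0.9672

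Cohort 1 conflict = P(toxicity breach) × P(u = 0); for example 0.3446 × 0.7351 = 0.2533. Cohort 2 gate taken alone = P(toxicity breach) × P(u ≤ 1); for example 0.3446 × 0.9672 = 0.3333.

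| | Toxicity 9.5% | 20% | 30% |
|---|---|---|---|
| Cohort 1, 2/6 a breach | 7.7% | 25.3% | 42.6% |
| Cohort 1, 2/6 allowed | 1.0% | 7.3% | 18.8% |
| Cohort 2 alone, 2/6 a breach | 10.1% | 33.3% | 56.1% |
| Cohort 2 alone, 2/6 allowed | 1.3% | 9.6% | 24.7% |

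Sensitivity at 20% toxicity: as unresectability goes from 2% (P(u = 0) = 0.8858) to 10% (0.5314), the Cohort 1 figure goes from 30.5% to 18.3% (2/6 a breach) or from 8.8% to 5.3% (2/6 allowed).

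The probability of exactly one unresectable patient in Cohort 1, where the gate and the 15% rule disagree, is 10.8% / 23.2% / 35.4% at unresectability of 2% / 5% / 10%.

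**4. Grade wording.** The gates and Section 4.4 say grade 3. Section 5.9 uses grade 3 or higher for replacement, and Section 6.3.2 records grade 3 and above. Taken literally, a grade 4 or 5 immune-related event does not count towards the gate.

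**The case against.** The best counter-argument is that the intent is clear. The stop sentences work as written, Section 4.4 names the 33% toxicity limit as the safety criterion, and Sections 2.1 and 2.2 speak of cohorts meeting milestones. A reasonable reader would drop SRT after a toxicity breach. On this view the fault is *or* written for *and* in two sentences. That is probably right about intent, but it is an inference, and no text gives the stop sentence precedence.

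Safety does not rest on the gates alone. Section 5.10 allows early termination for a potential health hazard, and Section 6.3.4 and Appendix 5 provide for monthly review of grade 3–5 events and DSMC notification. These limit the harm, but they are discretionary and do not say which gate sentence governs.

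On size, the objection has some force. If two of six is what 33% was meant to allow, the reference rate gives only 1.0% (Cohort 1) and 1.3% (Cohort 2). The Cohort 2 figures also take that gate alone. If Cohort 1 must first pass both limits at the same rates, 56.1% becomes 0.7351 × 0.4202 × 0.5608 = 17%, and 33.3% becomes 0.7351 × 0.6554 × 0.3333 = 16%.

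Replacement under Section 5.9 can raise the denominator of the 15% rule: 1/7 and 2/14 are both 14.3% and would not terminate. The rule is re-evaluated at each case, however, and 2/13 = 15.4% still terminates, so replacement would seldom change the result.

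Finally, a stricter study-wide stop beside a looser cohort gate is not in itself a contradiction, and the primary analysis is unaffected. Both points are fair.

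**Conclusion.** The concern holds. In both cohorts, a breach of the toxicity limit alone satisfies two sentences that order opposite actions. The rest of the protocol hints at the intended reading without stating it, and the 15% rule does not reach this case.

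The logical fault needs no assumptions. Its frequency does: under 5% unresectability and independence, the unresolved Cohort 1 conflict runs from 1.0% (9.5% toxicity, 2/6 allowed) to 42.6% (30% toxicity, 2/6 a breach). At the low end it is uncommon. The case for correcting it rests on consequence: these gates decide whether the study stops and whether patients may be randomised to SRT. It should be corrected before either gate is applied.

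The rounding of 33%, the missing grades 4–5 and the mismatch with the 15% rule are secondary, but they sit in the same sentences.

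**What to change.** In Section 2.2, for both cohorts, proceed only if the toxicity limit *and* the unresectability limit are met. Keep the stop sentences as they are: breach of either limit terminates the study (Cohort 1) or drops SRT (Cohort 2). In the same edit:

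1. State the toxicity limit as a number of patients out of 6.
2. Write grade 3 or higher in Sections 2.2 and 4.4, in line with Section 5.9.
3. Reconcile the gates with the 15% rule. The simplest way is to say that the 15% rule overrides them, and to change the Cohort 1 allowance of one unresectable patient and the Cohort 2 action at two so that they agree with it.

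Giving the 15% rule a minimum number of patients would loosen a safety stop. It is not needed for this repair. The values of the limits are for the sponsor and the DSMC to choose.

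The cost is a few words in two sections, plus the amendment approvals by the PRC and IRB that Section 9.4 requires. Sample size, procedures and the primary analysis do not change.

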#### 7.2 Statistical Analysis Plan

Sample size justification:

The sample size is based upon the anticipated number of patients who will have samples that will be useful for study of immunologic changes in the number of infiltrating CD3+ T cells/ $\mu\text{m}^2$  in the lung cancer tissue between the pre-treatment (baseline) biopsy and post-treatment thoracotomy specimens.

The sample size is fixed at 40 patients. It assumes successful accrual of 6 patients from each of the two run-in cohorts and an additional 28 patients from the randomized expansion cohort, for a total of 40 patients. However, past clinical experience indicates that as many as one-third of patients may not be able to complete a new successful core needle biopsy procedure and only prior archived tissues will be available for any analysis (which may eventually turn out to be insufficient to evaluate for primary endpoint). These patients who enrolled but whose core biopsy is later found to be inadequate after initiation of therapy will be allowed to continue on the protocol but will not be included in the primary endpoint.

The null hypothesis is that a two-fold increase will be seen in 15% of the evaluable 26 patients (assuming up to one third of samples may be unevaluable for primary endpoint). The alternative hypothesis is that a two-fold increase will be seen in 40% of the evaluable 26 patients. This yields 90% statistical power, with one sided 5% alpha level based on an exact binomial test.

The goal of achieving a two-fold increase in 40% of the evaluable population is a reasonable one, as estimated from a previous study showing greater-than-three-fold increase in 57% of patients when CD3+ T cells/ $\mu\text{m}^2$  were measured in prostate cancer tissue treated with a cell- based cancer immunotherapy, with a null hypothesis having been set at a two-fold increase in 15% of the population (Fong 2014). The current study includes immunotherapy +/- stereotactic radiation therapy, both of which are anticipated to create increased immunogenicity against NSCLC.

It is anticipated that accrual will be completed in 10 months (4 patients per month), with each patient treated for approximately 2.5-3 months and then followed for 12 months after completing protocol therapy. Total study duration is 25 months.

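### The 33% run-in toxicity limit matches no possible count out of six: 2 of 6 exceeds it as written but passes if 33% is a rounded one third, so the decision at exactly two events is undefined

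*Combined protocol and SAP*

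**What the plan says.** Section 2.2 fixes the size of both run-in cohorts. Cohort 1 is "6 patients. The patients will undergo 2 cycles of pembrolizumab prior to surgery", and Cohort 2 is "6 patients. The patients will undergo 2 cycles of pembrolizumab then within the week" of the second cycle, when SRT is given. Section 7.2 repeats the sizes: "It assumes successful accrual of 6 patients from each of the two run-in cohorts".

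Four sentences in section 2.2 act as gates, a proceed sentence and an adverse sentence for each cohort. The toxicity condition is at most 33% to proceed and more than 33% for the adverse branch. For Cohort 2 the adverse sentence begins "If >33% of patients in Cohort 2 experience grade 3 immune-related toxicity attributable to study interventions" and leads to this outcome: "then proceed to Expansion Cohort (parameters only of Cohort 1, e.g. preoperative pembrolizumab alone". For Cohort 1 the adverse sentence ends "patient progresses to unresectability over the course of study treatment, the study will terminate".

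Each gate has a second condition, on unresectability. That one is written as a count: at most one patient, or more than one. In all four sentences the two conditions are joined by *or*.

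Section 4.4 restates the toxicity criterion, again as at most 33%, in the sentence that begins "Secondary objectives include safety according to criteria described by the protocol". Section 5.9 adds that "patients who come off study before completing surgery without grade" 3 or higher toxicity will be replaced.

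**The concern.** With six patients the observed rate can take only seven values, and the stated limit lies a third of a percentage point below one of them. Two events in six is an ordinary result for a run-in, and at that result the text supports two opposite readings. If one third was meant to be tolerable, the written limit fails at its own boundary. If only one event was meant to be tolerable, 33% is a misleading way to write 1 of 6, which is 16.7%.

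What depends on it is whether the trial continues after Cohort 1, and whether SRT and the randomised comparison survive Cohort 2. The trial is open label (section 5.2.3), so the number of events will be known when someone decides how to read 33.3%. A safety gate should not be interpreted after its data are in.

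**Working it through.** **Inputs.** Cohort size 6 (sections 2.2 and 7.2). Limit 33%, with no count and no rounding rule (sections 2.2 and 4.4). The plan gives no target toxicity rate, error rate or operating characteristics for this gate, so there is no stated figure to reproduce, and the true rates used below are assumptions.

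**Step 1: which counts meet the limit.** 33% of 6 is 0.33 × 6 = 1.98 patients, so no whole number of patients equals the limit.

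| Events of 6 | Rate | Above 33% as written? | Above one third, or above 33% after rounding to whole percent? |
|---|---|---|---|
| 0 | 0% | no | no |
| 1 | 16.7% | no | no |
| 2 | 33.3% | **yes** | **no** |
| 3 | 50.0% | yes | yes |
| 4 to 6 | 66.7% or more | yes | yes |

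The readings disagree in one row only. As written, two events trigger the adverse branch; as a rounded one third, three are needed.

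**Step 2: how often the disagreement matters.** With X ~ Binomial(6, p), P(X ≥ r) is the sum over k from r to 6 of C(6,k) p^k (1−p)^(6−k). At p = 0.20:

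- P(0) = 0.8^6 = 0.26214
- P(1) = 6 × 0.2 × 0.8^5 = 0.39322
- P(2) = 15 × 0.2² × 0.8^4 = 0.24576
- P(X ≥ 2) = 1 − 0.26214 − 0.39322 = 0.34464
- P(X ≥ 3) = 0.34464 − 0.24576 = 0.09888

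The same calculation across the assumed range, per cohort and for the toxicity limb only:

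| Assumed true rate | Trigger at 2 or more | Trigger at 3 or more | Exactly 2 (readings conflict) |
|---|---|---|---|
| 10% | 11.4% | 1.6% | 9.8% |
| 20% | 34.5% | 9.9% | 24.6% |
| 30% | 58.0% | 25.6% | 32.4% |
| 40% | 76.7% | 45.6% | 31.1% |

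The nearest rate in the documents is 47 of 495 (9.5%) with grade 3 or higher adverse events, in the KEYNOTE-001 summary in section 4.1.2. It comes from advanced disease without surgery or SRT and is not restricted to immune-related events, so it is illustrative only. At 9.5% the chances are 10.5% against 1.4%.

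**Step 3: the denominator.** These results need six patients in the denominator. If a replaced patient were also counted, making seven, 2/7 = 28.6% would pass on either reading and 3/7 = 42.9% would fail on either. The ambiguity would vanish, but only because of an unstated choice.

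**The case against.** The strongest reply is that this is notation rather than error. The written rule has a definite cut-off, since 33.33 is greater than 33. Percentages are commonly given as whole numbers, and 2/6 rounds to 33%. The authors wrote a count where one patient was the limit (unresectability), so a one-event toxicity limit would naturally have been written that way too; the likely intent is therefore two of six. That inference is reasonable, but it is an inference, and it contradicts the literal text. A rule with a definite literal meaning and a different probable meaning still has to be settled before it is used.

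Three limits on the point do stand.

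- **A reader might infer that two toxicities end the study as written. The documents do not establish that.** Because the proceed sentence uses *or*, two toxicity events with at most one unresectable patient satisfy both the proceed sentence and the adverse sentence. This is a separate defect in the same sentences. Correcting it would still leave 2 of 6 undecided.
- **A reader might take the figures above as the chance that a cohort fails or passes. They are not.** They leave out the unresectability limb and the cumulative 15% stopping rule. For scale, at 20% toxicity the chance that both cohorts clear the toxicity limb is 0.655² = 43% or 0.901² = 81%, assuming equal rates and independence. If both limbs must be met, the limbs are independent and true unresectability is 5%, these become about 40% and 76%; at 15% unresectability, about 26% and 49%.
- **The denominator is assumed.** Section 5.9 tends to keep it at six but does not define it.

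The figure in section 2.2 was not available in the text reviewed, so whether it shows a count could not be checked.

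**Conclusion.** The point holds in a bounded form. The run-in toxicity limit corresponds to no attainable count in a six-patient cohort, and the text of sections 2.2, 4.4, 5.9, 7.1 and 7.2 and Appendix 5 gives neither a count nor a rounding rule. The readings conflict only at exactly 2 of 6, an outcome with probability 9.8% to 32.4% per cohort over assumed true rates of 10 to 40%. There, the toxicity-limb decision reverses. It would go too far to say that the trial's main decisions generally turn on rounding: at every other count out of six the two readings agree.

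The size rests on six evaluable patients per cohort, independent events, assumed true rates and the toxicity limb alone. The arithmetic that 2/6 lies above 33% and rounds to 33% needs only the denominator of six.

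**What to change.** In the four gate sentences of section 2.2, and in section 4.4, replace the percentage with the number of patients that the sponsor and its safety committee intend. Give the denominator explicitly, for example six evaluable patients, and say how patients replaced under section 5.9 count. In the same edit, reconcile the *or* that joins the toxicity and unresectability conditions, so that no result can satisfy both the proceed and the adverse sentence. If the figure in section 2.2 carries the limit, align it.

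If operating characteristics are added, label them as toxicity limb only or recompute them with the unresectability limb included. Which count is acceptable is not a matter for this review.

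The cost is wording only, with no change to sample size or procedures. The stated tolerance may look stricter or looser than 33% does now. The edit is best made before either cohort has two events, so that the reading is not chosen with the result in view.
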